4. OBJECTIVES AND OUTCOME MEASURES/ENDPOINTS

4.1. Primary Objective

The primary objective of the study is to determine whether the FMW programme reduces cancer-specific distress.

4.2. Secondary Objectives

Secondary objectives of the study including determining the effects of the FMW programme on anxiety, depression, and general stress, determining the effects of the FMW programme on quality of life, determining the effects of the FMW programme on psychological adjustment to cancer, determining the effects of the FMW programme on health service utilisation, determining whether social support, vulnerability to distress, and motivation to seek information moderate the effects of the FMW programme on primary and secondary study endpoints, and determining whether psychological flexibility mediates the effect of the FMW Programme on cancer-specific distress. We will also conduct exploratory analyses testing the potential moderating effects of clinical and demographic variables on primary and secondary endpoints.

4.3. Primary Endpoint

Cancer-specific distress, as measured by the Post-Traumatic Stress Scale (Foa et al., 1993).

4.4. Secondary Endpoints

Secondary endpoints of the study include depression, anxiety, and stress, as measured by the Depression, Anxiety, and Stress Scales – 21 item version (DASS-21) (Lovibond & Lovibond, 1996); quality of life, as measured by the The European Organisation for Research and Treatment of Cancer Core Quality of Life Questionnaire (version 3.0) (QLQ-C30) (Aaronson et al., 1993); psychological adjustment to cancer, as measured by the Psychological Impact of

Cancer (PIC) Scale (Hulbert-Williams et al., 2019); and health service utilisation, as measured by the UK Cancer Costs Questionnaire.

5. STUDY DESIGN

Patient Identification and Approach

Clinical Research Network staff at participating sites will screen clinical data to identify patients who meet all inclusion criteria and no exclusion criteria for the study. Where the next scheduled appointment is over 6 weeks into the future, staff will conduct patient approach over the telephone. Where eligible patients have an appointment scheduled within the next 6 weeks, Clinical Research Network staff will introduce the study either in person at a scheduled hospital appointment or via a telephone conversation. Though face-to-face discussion is preferred for patients who have an appointment scheduled within the next 6 weeks, CRN staff may use their own discretion in choosing the best approach method for each patient. Approached patients will be provided with a hard-copy information pack about the clinical trial and given the opportunity to ask questions about the study.

Informed Consent and Baseline Assessment

Information packs provided to participants will contain the link for an online survey. This online survey will present the Participant Information Sheet and allow participants to provide informed consent online via an e-consent form. Based on our assessment that this study poses minimal risk to participants, we have deemed that a simple electronic signature, consisting of typewritten initials, a typewritten name and date of birth is a sufficient indication of informed consent, as per the Health Research Authority's joint statement on seeking consent by electronic methods (https://www.hra.nhs.uk/media/documents/hra-mhraeconsent-statement-sept-18.pdf). Participants will be asked whether they would prefer to complete study questionnaires online or in hard-copy (pen-and-paper) form. Participants will also be asked whether they would prefer to receive study reminders via text or phone call. After submitting their e-consent form, participants will be provided with access to the baseline questionnaire assessing demographic characteristics, baseline cancer-specific distress, anxiety, depression, and general stress, quality of life, psychological adjustment to cancer, health service utilisation, social support, vulnerability to distress, motivation to seek information, and psychological flexibility. For all questionnaires in this study, participants will either be directed to complete this questionnaire online or the research team will post a paper questionnaire pack to them, including a pre-paid return envelope, as per the preference indicated by the participant in their consent form. Participants will be given the option to complete questionnaires in more than one sitting in order to reduce participants' burden. Where a participant has submitted their completed e-consent form but not completed the baseline questionnaire, a member of the study team will send the participant a reminder to complete the baseline questionnaire one week after the e-consent form has been received.

A member of the research team will then send the participant an email confirming receipt of their informed consent form and outlining the next stages of the study. The same member of the research team will add each participant's details to the Contact Details database and securely send a copy of each participant's consent form and information regarding the

handling of adverse events to the recruiting site. A staff member from the Clinical Research Network will subsequently log that participant's participation in the study in their patient records.

If consent has not been confirmed two weeks after a patient has expressed interest in the study, a staff member from the Clinical Research Network will follow up with that patient to remind them of the study.

Staff members from the Clinical Research Network will send a log of screening and patient approach activities undertaken to the research team on a fortnightly basis. This log will not contain personally identifiable information relating to patients who have not consented to take part in the study. A member of the research team will update a database of recruitment uptake data accordingly.

Randomisation

Prior to the beginning of the study, the LCTC will create the randomisation code for the study and set up a randomisation portal to be used by the research team. This system will be set up such that each participant in the study will be randomised to either the active intervention arm of the study or the waitlist control arm in a 1:1 ratio. Following the receipt of each participant's baseline questionnaire, an unblinded member of the research team will conduct randomisation for that participant and log their group allocation in a password-protected randomisation key. For participants in the intervention arm of the study, an unblinded member of the research team will then match each participant with a random username and temporary password combination. An unblinded member of the research team will then activate this participant's account, which will trigger an automatic welcome email to be sent to the participant. The welcome email will contain the participant's username and temporary password, as well as instructions for accessing the FMW website. This member of the research team will also email the participant directly to inform them of their group allocation and to explain the next steps in the study. For participants in the waitlist-control arm, the unblinded research team member will subsequently email the participant to inform them of their allocation to the waitlist-control condition and provide them with an information pack about existing support and cancer survivorship services in the UK. An unblinded member of the research team will check for new participant log-ins each week and provide a text or phone call reminder if the participant has not logged into the website by Week 2. The mid-point assessment, post-treatment assessment, 3-month follow-up assessment and 6-month assessment will be scheduled from the date of being informed of treatment allocation.

Finding My Way UK Programme

The first time that a participant logs in to the FMW website, the website will open on a welcome page, which will immediately play a video describing an overview of the FMW programme and website functionality. Participants will be able to decide the order in which they complete each of the 6 programme modules. Participants will have the opportunity to change this order at any point in the programme, provided that the module being changed has not already been released to the participant. If participants do not change the order of

module release, the modules will be released in a standard order decided in advance by the research team.

At the beginning of each week, a new cognitive-behavioural therapy-based module will be made available to participants in the active treatment arm, in the order that participants requested. Participants will receive an email reminder about the new available module at this time. Participants in the intervention group will receive an additional text or phone call reminder (depending on their stated communication preference) if they haven't logged in one week after account activation, and an additional phone call reminder if they haven't logged in two weeks after account activation. Module 1 of FMW focuses on orientation to the treatment team, information about complementary therapies, and decision-making. Module 2 focuses on managing physical symptoms and cognitive changes through activity monitoring, relaxation, and meditation. Module 3 focuses on emotion regulation and stress management. Module 4 focuses on issues around cancer and identity. Module 5 focuses on managing relationships with family and friends. Module 6 focuses on transitioning to life after cancer.

Mid-point assessment

At the end of the third week after being informed of their allocation to the waitlist-control or intervention group, the research team will send participants questionnaires assessing cancerspecific distress; anxiety, depression, and general stress; quality of life; psychological adjustment to cancer; health service utilisation; and psychological flexibility. Participants will receive a text or phone call reminder (depending on their stated communication preference) if they have not completed this survey after one week. Participants will receive an additional phone call reminder if they have not completed the survey after two weeks. The research assistant will offer participants the option to complete the survey via telephone at this time, if they prefer. If participants choose to complete the mid-point assessment via telephone, the research assistant will complete the Qualtrics survey for them, according to the participant's telephone responses.

Compliance Assessment

An unblinded member of the research team will check each week for new logins to participants' sixth and final module. Once each participant has commenced their sixth module, this member of the research team will send them a survey containing the Self-Help Compliance Scale to complete. Participants will receive a text or phone call reminder (depending on their stated communication preference) if they have not completed this survey after one week. Participants will receive an additional phone call reminder if they have not completed the survey after two weeks. The research assistant will offer participants the option to complete the survey via telephone at this time, if they prefer. If participants choose to complete the compliance assessment via telephone, the research assistant will complete the Qualtrics survey for them, according to the participant's telephone responses.

Post-treatment assessment

At the end of the sixth week after being informed of their allocation to the waitlist-control or intervention group, the research team will send all participants a series of questionnaires assessing cancer-specific distress; anxiety, depression, and general stress; quality of life;

psychological adjustment to cancer; health service utilisation; and psychological flexibility. A member of the research team will follow up with a text or phone call reminder (depending on the participant's stated communication preference) after one week if the participant has not completed the survey at this time. Participants will receive an additional phone call reminder if they have not completed the survey after two weeks. The research assistant will offer participants the option to complete the survey via telephone at this time, if they prefer. If participants choose to complete the post-treatment assessment via telephone, the research assistant will complete the Qualtrics survey for them, according to the participant's telephone responses.

Booster Module

One month after completing the six-week FMW programme, participants in the intervention arm will be provided access to an additional booster module. This booster module summarises key programme strategies, sign-posts participants to content in the first six modules that may be useful to them at this stage, and includes some additional text and video content related to life after cancer. Participants will be notified of this booster module via email. An unblinded member of the research team will send a text or phone call reminder (depending on the participant's stated communication preference) after one week if the participant has not logged into the FMW programme by this time.

3-month follow-up assessment

Three months after receiving the link to the post-treatment assessment, participants will be sent a series of questionnaires assessing cancer-specific distress; anxiety, depression, and general stress; quality of life, psychological adjustment to cancer, health service utilisation, and psychological flexibility. A member of the research team will follow up with a text or phone call reminder after one week (depending on the participant's stated communication preference) if the participant has not completed the survey at this time. Participants will receive an additional phone call reminder if they have not completed the survey after two weeks. The research assistant will offer participants the option to complete the survey via telephone at this time, if they prefer. If participants choose to complete the 3-month follow-up assessment via telephone, the research assistant will complete the Qualtrics survey for them, according to the participant's telephone responses.

6-month follow-up assessment and debrief

Six months after receiving the link the post-treatment assessment, participants will be sent a series of questionnaires assessing cancer-specific distress; anxiety, depression, and general stress; quality of life, psychological adjustment to cancer, health service utilisation, and psychological flexibility. A member of the research team will follow up with a text or phone call reminder after one week (depending on the participant's stated communication preference) if the participant has not completed the survey at this time. Participants will receive an additional phone call reminder if they have not completed the survey after two weeks. The research assistant will offer participants the option to complete the survey via telephone at this time, if they prefer. If participants choose to complete the 6-month follow-up assessment via telephone, the research assistant will complete the Qualtrics survey for them, according to the participant's telephone responses. After the participant completes the

6-month follow-up assessment, a member of the research team will debrief the participant. Where a participant has not completed the 6-month follow-up assessment, they will instead be debriefed one month from the date on which they were sent the 6-month follow-up questionnaire pack. An unblinded of the research team will activate the account of participants in the waitlist-control arm at this time. Participants in the waitlist-control arm will then proceed through the intervention modules in exactly the same manner as described above for participants in the intervention arm.

Clinical Data Collection

At the time point when each participant receives access to the 6-month follow-up assessment, a member of the research team will contact the referring Clinical Research Network staff member to request the following clinical data:

- Date of diagnosis;
- Primary or recurrent cancer;
- Whether the participant was treated with curative or palliative intent;
- The treatment approach adopted for the participant (surgery, chemotherapy, radiotherapy, or watch-and-wait);
- Date of the end of active treatment (if treatment has ended at this point);
- The date of any recurrence or relapse (if applicable);
- Date of death (if applicable);
- Whether the participant received referral to a mental health care professional since their diagnosis of cancer;
- The number of days of inpatient care since study enrolment, and types of healthcare professionals seen during these stays;
- The number of outpatient visits since study enrolment, and types of healthcare professionals seen during these visits; and
- Any diagnosis tests conducted since study enrolment.

The Clinical Research Network staff member will complete a standardised Clinical Data Extraction Form containing fields for the above points of information. The Clinical Research Network staff member will then send this form securely to the research team via an encrypted email attachment or an encrypted email. A member of the research team will then add these data to a Clinical Data database. A member of the research team will follow up with the Clinical Research Network if these data have not been received two weeks after the data request.

Qualitative data collection

Following participant debriefing for the quantitative component of the clinical trial, we will purposively recruit 20-30 trial participants in the intervention arm of the study representing a range of ages, gender, cancer types, and degree of website engagement to take part in qualitative interviews assessing the acceptability, and intervention factors that affect the acceptability, of the FMW online programme. An unblinded member of the research team will call participants in the intervention arm after they have been debriefed for the quantitative component of the clinical trial to verbally explain the qualitative component of the study and seek expressions of interest. If the participant does not answer the phone, the

unblinded member of the research team will not leave a voicemail, but will attempt to reach them via telephone two more times. If the unblinded member has not been able to reach them via telephone after three attempts, the research assistant will email the participant instead to gauge their interest in the qualitative sub-study.

An unblinded member of the research team will subsequently email the Participant Information Sheet and consent form for the qualitative interview to participants who have expressed an interest in participating in this component of the study. If the participant does not respond within two weeks, the same member of the research team will follow up with an email prompt. This unblinded member of the research team will coordinate the qualitative interview, answer any additional questions the participant may have and collect the participant's completed consent form. Participants will be given the option to either complete the qualitative interview in-person (either at the University or in their own home) or via a telephone or video call. The researcher conducting the qualitative interview will not be made aware of the participant's name or participant number, and will thus remain blinded for the purposes of subsequent data analysis. This interview will be audio-recorded for later transcription. The unblinded member of the research team will subsequently debrief the participant. Any participant travel expenses will be reimbursed.

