8.8.2. Post-Traumatic Stress Scale

The Post-Traumatic Stress Scale (Foa et al., 1993) is a 17-item measure of cancer-specific distress. Participants respond on a 4-point Likert scale, where responses are anchored from 0 (Not at all or only one time) to 3 (5 or more times per week / almost always). The Post-Traumatic Stress Scale is associated with excellent internal consistency reliability (α = .91) (Foa et al., 1993). The post-traumatic stress scale has good concurrent validity, including

strong positive correlations with other measures of trauma-related intrusion and avoidance, anxiety, and depression (Foa et al., 1993).

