8.8.3. DASS-21

The Depression, Anxiety, and Stress Scales, 21-item version (DASS-21) (Lovibond & Lovibond, 1996) is a short measure of negative emotions experienced over the course of the past week for the individual. Each item is presented as a 4-point Likert scale, anchored as 0 ("Did not apply to me at all"), 1 ("Applied to me some degree, or some of the time"), 2 ("Applied to me to a considerable degree or a good part of the time"), and 3 ("Applied to me very much or most of the time"). The total score for each subscale of the 21-item DASS-21 is calculated by summing participants' responses to the items for each subscale and multiplying this sum by two. Higher scores for each subscale therefore indicate greater levels of depression, anxiety, and stress, respectively. The depression scale of the DASS-21 is associated with excellent internal consistency reliability (α = .91) (Lovibond & Lovibond, 1995). The anxiety scale and the stress scale of the DASS-21 are both associated with good internal consistency reliability (α = .81 and α = .89, respectively) (Lovibond & Lovibond, 1995). The DASS-21 has good concurrent validity, including strong, positive correlations with other measures of depressive symptoms and anxiety (P. F. Lovibond & Lovibond, 1995).

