8.8.4. QLQ-C30

The QLQ-C30 (Aaronson et al., 1993) is a 30-item quality of life assessment for cancer patients, which yields a global quality of life score and five functional subscale scores associated with physical, emotional, social, role, and cognitive quality of life domains. The global score for the QLQ-C30 is associated with good internal consistency reliability (α = .86) (Aaronson et al., 1993). The QLQ-C30 is associated with good concurrent validity, with global quality of life and the role functioning and physical functioning scales significantly positively correlated with performance status throughout treatment (Aaronson et al., 1993). The QLQ-C30 score can be converted into an indication of QUALYs to be used in health economic analysis.

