8.8.5. The PIC

The PIC (Hulbert-Williams et al., 2019) is a 12-item self-report measure of psychological adjustment to cancer. Each item is presented on a 4-point Likert scale anchored from "Definitely does not apply" to "Definitely does apply". The PIC yields four subscale scores: Cognitive Distress, Cognitive Avoidance, Emotional Distress, and Fighting Spirit. For the purposes of the current study, we will only analyse the Cognitive Distress, Cognitive Avoidance, and Emotional Distress subscales. All subscales are associated with at least fair internal consistency reliability ($\alpha > .623$) and good concurrent validity with longer measures of psychological adjustment to cancer (Hulbert-Williams et al., 2019).

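### The two-week telephone call offers the whole follow-up survey (at least 103 items) and does not tell the assistant to secure the 17-item primary scale first or alone

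*Protocol*

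**What the plan says.** Protocol section 5 sets the same sequence at mid-point, post-treatment, 3 months and 6 months. A non-responder gets a text or telephone reminder at one week and a telephone call at two weeks. On that call, "The research assistant will offer participants the option to complete the survey via telephone at this time, if they prefer". The post-treatment paragraph adds: "If participants choose to complete the post-treatment assessment via telephone, the research assistant will complete the Qualtrics survey for them". The 3-month paragraph matches it: "If participants choose to complete the 3-month follow-up assessment via telephone, the research assistant will complete the Qualtrics survey for them". No later data-collection contact is described for any of the four assessments.

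Sections 8.7.3 and 8.7.5 to 8.7.7 define the survey at each of these times as six instruments: the Post-Traumatic Stress Scale, DASS-21, QLQ-C30, PIC, UK Cancer Costs Questionnaire and CompACT. Section 4.3 makes the first of these the primary endpoint. Section 8.8.2 says that it "is a 17-item measure of cancer-specific distress".

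Three other provisions bear on the point. Section 5 (Informed Consent and Baseline Assessment) lets participants spread questionnaires over more than one sitting. Section 8.9 lets them skip questions, with a warning that this may keep them out of an analysis. Section 11.2.3 plans a mixed model for repeated measures, with sensitivity analyses for missing data.

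**The concern.** The two-week call is the last planned chance to obtain the primary outcome from someone who has not responded to the initial request or the one-week reminder. What it puts to that person is the same long battery, only in another mode. Someone willing to give a few minutes, but not to answer more than a hundred questions by telephone, is not offered anything shorter.

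Two things are at stake. The first is precision, since section 11.1 already budgets for 20% attrition. The second is bias. A mixed model handles missing visits well if non-response is explained by the data already observed. Where the questionnaire measures distress and participants know their allocation, non-response may well depend on current distress or engagement. Scores recovered at this call come from the people about whom that assumption is most doubtful.

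**Working it through.** **Length of the survey.** The item counts are the protocol's own:

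| Instrument | Items | Section |
|---|---|---|
| Post-Traumatic Stress Scale (primary) | 17 | 8.8.2 |
| DASS-21 | 21 | 8.8.3 |
| QLQ-C30 ("is a 30-item quality of life assessment for cancer patients") | 30 | 8.8.4 |
| PIC ("is a 12-item self-report measure of psychological adjustment to cancer") | 12 | 8.8.5 |
| CompACT | 23 | 8.8.10 |
| UK Cancer Costs Questionnaire | not stated | 8.8.6 |

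17 + 21 + 30 + 12 + 23 = 103, a lower bound because the cost questionnaire is uncounted. The primary scale is at most 17/103 = 16.5% of the items.

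**The plan's own sample size (section 11.1).** SD of change = 7 × √(2 × (1 − 0.7)) = 5.42. With the paired formula, n = (5.42 × (1.960 + 0.842) / 1.4)² = 117.6. Allowing for 20% attrition, 117.6 / 0.80 = 147.05, so 147 per arm and 294 in total. The stated figure is reproduced.

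**What a primary-only fallback could recover.** Planned losses are 294 × 0.20 = 58.8 participants. The protocol does not say what share of them a shorter request would bring back, so a recovery share r is assumed:

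- evaluable per arm: n = 147 × (1 − 0.20 × (1 − r))
- standard error of the difference in mean change: 5.42 × √(2/n)
- power for 1.4 units: by the protocol's paired basis, and by a two-sample comparison of change

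| r (assumed) | Recovered, total | n per arm | SE | Fall in SE | Power, paired | Power, two-sample |
|---|---|---|---|---|---|---|
| 0 | 0 | 117.6 | 0.707 | – | 0.79 | 0.51 |
| 10% | 5.9 | 120.5 | 0.698 | 1.2% | 0.80 | 0.52 |
| 25% | 14.7 | 125.0 | 0.686 | 3.0% | 0.82 | 0.53 |
| 50% | 29.4 | 132.3 | 0.666 | 5.7% | 0.84 | 0.56 |

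On either basis the gain in power is below five percentage points, even at r = 50%. The gap between the two power columns comes from using a paired formula for a comparison of two arms. It is a separate matter, and this point does not depend on it.

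**Time left after the call.** The mid-point survey goes out at the end of week 3, so its call falls at about week 5, one week before the post-treatment battery. At 6 months, non-completers are debriefed one month after the pack was sent, and waitlist accounts are activated at that point. That leaves about two weeks after the call before a waitlist score stops being a clean control value.

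**The case against.** The strongest case against is that the protocol does not make the battery all-or-nothing. Telephone is an optional mode, so declining it is not declining the survey. Online or paper return stays open, and no closing date is stated. Split sittings and skipped questions are allowed, so a participant who gave only the 17 items would break no rule. The primary scale is already listed first among the outcome instruments in every follow-up list, though nothing says that the list is the order of administration. A person who misses one visit still contributes baseline and other visits to the mixed model. Section 8.10 allows up to 30% over-recruitment to offset missing data: 294 × 1.30 = 382, and 382 × 0.80 is about 306 evaluable, against 294 × 0.80 = 235 as planned. That far exceeds what the fallback could regain.

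Most of this stands, and it limits the claim. A reader might infer that refusing the call forfeits the primary outcome. The documents do not support that: the loss is a likely consequence for some participants, not one that the protocol fixes.

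A reader might also work out a bias. If the arm difference among non-responders departed from that among responders by 1.4 to 3.5 points (0.2 to 0.5 of the SD of 7, assumed), 20% missing would shift the estimate by 0.20 × 1.4 = 0.28 to 0.20 × 3.5 = 0.70. That describes a responder-only estimate, not the planned mixed model, and the departure itself has no source in the protocol. Nor can it be supposed that attrition would be halved. The 20% is not broken down, and it can include withdrawal, death and participants who cannot be reached, none of whom a shorter request recovers.

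What the objection does not remove is that the assistant is given no instruction to secure the primary scale, and that section 8.9 warns participants against partial completion. Over-recruitment restores numbers but not representativeness, and sensitivity analyses can only examine the damage afterwards.

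**Conclusion.** The point holds as an inexpensive improvement to trial conduct, not as an error in the design. The item counts, the timing of the call and the absence of a primary-first instruction all rest on the protocol's own text. A late responder who will not complete the full battery is at risk of having no primary score at that visit.

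The benefit is real but modest: about 3 to 15 more evaluable participants per arm and a standard error about 1% to 6% smaller, if between 10% and 50% of planned losses were recovered. That range is an assumption, and its upper end is favourable. The bias argument is qualitative: recovered scores would come from the group most likely to differ, but the document offers nothing from which to size the effect.

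**What to change.** In the mid-point, post-treatment, 3-month and 6-month paragraphs of section 5, state that at the two-week call the full survey is offered with the Post-Traumatic Stress Scale asked first, and that this scale is accepted alone only if the participant declines the rest. Confirm that the scale comes first in the online and paper packs, and record the mode of completion.

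The cost is a few sentences and a call script. The call already takes place, and no planned visit or figure changes. The downside is that a few participants offered the short option might otherwise have completed the secondary, mediator (CompACT) and cost measures. Offering the full survey first keeps that loss small.
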